## PART 1: TRIAL-RELATED PART OF THE PROTOCOL

### 1. Title of the trial

Efficacy of golimumab in early axial spondyloarthritis (axSpA) in relation to gut inflammation, an early remission induction study (GO GUT).

### 2. Trial number

Protocol: AGO/2017/004

EudraCT number: 2017-001728-23

### 3. Objectives and hypothesis

#### 3.1 Primary objectives

1. To describe and confirm the relationship between subclinical gut inflammation and axSpA.
2. To evaluate whether there is a higher need of anti-tumor necrosis factor  $\alpha$  (anti-TNF $\alpha$ ) treatment in axSpA patients with (subclinical) gut inflammation compared to those without.

#### 3.2 Secondary objectives

1. To describe the clinical response of a treat-to-target principle in early axSpA and explore the possibility of drug-free remission.
2. To evaluate the relation between the presence of (subclinical) gut inflammation and the therapeutic response to anti-TNF $\alpha$  in patients with axSpA.
3. To evaluate the relationship between (subclinical) gut inflammation on the one hand and remission induction and relapse on the other hand in patients with axSpA.

#### 3.3 Hypothesis

The hypothesis of the study is that the presence of (subclinical) gut inflammation at baseline in patients with early active axSpA predisposes to a more severe disease defined as more need to use anti-TNF $\alpha$  therapy and a shorter time to relapse after stopping anti-TNF $\alpha$  therapy after obtaining sustained clinical remission. Overall, we hypothesize that subclinical gut inflammation is an important predictor in therapy response and outcome. These data could provide us better insights into the complex interactions between gut and joint inflammation and guide us in the therapeutic approach.

#### 3.4 Primary endpoint and timepoint of the endpoint.

Clinical remission, evaluated on 2 consecutive follow-up visits (interval: 12 weeks).

### **3.5 Secondary endpoint and timepoint of the endpoint.**

Mucosal healing, evaluated by ileocolonoscopy at time of clinical remission.

#### **4.2 Sponsor**

Ghent University.

#### **4.3 Funding**

Research grant by Merck Sharp & Dohme (MSD).

Golimumab will be provided by MSD.

### **5. Introduction**

Spondyloarthritis (SpA) is an immune-mediated, inflammatory rheumatic disease concept, consisting of a group of different diseases, sharing common genetic, clinical and radiological characteristics.

Patients develop inflammatory back pain and/or pauci-articular peripheral arthritis/enthesitis. In the long term, chronic inflammation of the axial skeleton can cause osteoproliferation and ankylosis of sacroiliac joint and spine.

An important feature of SpA is the frequent association with extra-articular symptoms such as anterior uveitis, psoriasis and inflammatory bowel disease (IBD), especially Crohn's disease (CD) and to a lesser extent ulcerative colitis [1]. About 50% of SpA patients have microscopic signs of bowel inflammation, without gastrointestinal symptoms. These microscopic lesions can be indistinguishable from lesions seen in early CD, suggesting that these might represent a subclinical form of the disease. Even more, IBD and SpA might be two ends of the same disease spectrum. This hypothesis is further strengthened by the identification of common genetic susceptibility factors linking SpA and IBD pathogenesis [2-4]. Hence, gut involvement seems to be important for SpA pathogenesis. A clear clinical relationship between gut and joint inflammation with remission of the latter being associated with disappearance of the first and vice versa is shown in the past [5-7]. Interestingly, patients with chronic gut inflammation showed a higher risk of evolving to ankylosing spondylitis (AS) and were more likely to start anti-TNF $\alpha$  therapy. Furthermore, they seem to respond better to the treatment with biologicals. This underlines the potential clinical implications of microscopic gut inflammation in SpA and suggests that gut inflammation predisposes to a more extensive, persistent disease [unpublished data; 7,8]. In addition, results from the Ghent Inflammatory Arthritis and spondylitis (GIANT) cohort showed that chronic gut inflammation is linked to more extensive bone marrow

edema of the sacroiliac joints on magnetic resonance imaging (MRI) [9]. It has also been suggested that inducing mucosal healing is an important factor for long-term remission [10].

In 2017 the Assessment of Spondyloarthritis international Society (ASAS) and the European League Against Rheumatism (EULAR) published an update of the axSpA treatment guidelines. In this update ASAS and EULAR stress on the importance of installing a treat-to-target principle. However, they do not suggest a preferred target, but leave the decision to the clinician and his patient. All patients should be treated with 2 different non-steroidal anti-inflammatory drugs (NSAIDs) during 4 weeks in total, before switching to an anti-TNF $\alpha$  agent. This period is significantly shorter than the previous recommendation of 3 months treatment with NSAIDs [11].

Golimumab is a fully human monoclonal antibody that binds and inhibits TNF $\alpha$  [12,13]. In Europe it is used, among others, in AS and non-radiographic axSpA who do not respond to NSAIDs. The effectiveness of golimumab is also shown in IBD [14]. Two randomized clinical trials (RCTs) have examined the therapeutic effects of golimumab in patients with SpA: the GO-RAISE and GO-AHEAD trial. Both trials showed a better ASAS 20 response at week 14 and 16, respectively, in the golimumab group compared to placebo. Clinical improvement was already seen 4 weeks after first subcutaneous administration of the medication. The treatment response was higher in patients with overt signs of inflammation, i.e. sacroiliitis on MRI and/or higher C-reactive protein (CRP) levels, than in patients without detectable inflammation. Thus, objective signs of inflammation could be a good predictor of treatment response. In terms of effect on imaging it showed that both sacroiliac joint and spine inflammation is reduced when treated with golimumab [15,16]. The safety profile of golimumab is comparable with that of other TNF $\alpha$ -inhibitors and is generally well-tolerated by patients.

## 6. The present study

### 6.1 Participants

#### 6.1.1 Number of participants

The total number of patients needed is estimated to be 147 (cfr. infra: 10.1 Calculation of the sample size). The subjects will be recruited through the department Rheumatology of the Ghent University Hospital, at the Reuma Institute in Hasselt, and at the Imelda hospital in Bonheiden.

#### 6.1.2 Inclusion criteria

In this trial we will include 147 subjects for which all of the following criteria must be met:

- Subject must have a diagnosis of axSpA and classified according to ASAS criteria.
- Subject is between 18 and 46 years at the screening visit.
- Subject has at least 3 months and maximum 1 year (almost) daily chronic back pain.
- Subject has an active disease defined as a positive MRI (according to ASAS definition) or elevated CRP (in patients who are HLA-B27+) and an ASDAS score > 2.1 (at least high disease activity).

### 6.1.3 Exclusion criteria

- Full anti-inflammatory dose of NSAIDs for more than 4 weeks for the duration of the axSpA symptoms.
- Prior exposure to any biologic therapy with a potential therapeutic impact on SpA, including anti-TNF therapy.
- Exposure to disease-modifying drugs (DMARDSS; i.e. methotrexate and sulfasalazine) in the last 3 months before the ileocolonoscopy.
- Exposure to systemic corticosteroid treatment in the last 14 days before the ileocolonoscopy.
- Infection(s) requiring treatment with intravenous antibiotics/antivirals/antifungals within 30 days prior to the baseline visit or oral antibiotics/antivirals/antifungals within 14 days prior to the baseline visit.
- Have a known hypersensitivity to human immunoglobulin proteins or other components of golimumab.
- History of central nervous system (CNS) demyelinating disease or neurologic symptoms suggestive of CNS demyelinating disease.
- History of listeriosis, histoplasmosis, chronic or active hepatitis B infection, hepatitis C infection, human immunodeficiency virus (HIV) infection, immunodeficiency syndrome, chronic recurring infections or active tuberculosis.
- Have a history of, or concurrent, chronic heart failure, including medically controlled, asymptomatic congestive heart failure.
- Evidence of dysplasia or history of malignancy (including lymphoma and leukemia) other than a successfully treated non-metastatic cutaneous squamous cell or basal cell carcinoma or localized carcinoma in situ of the cervix.
- Have received, or are expected to receive, any live virus or bacterial vaccination within 3 months prior to the first administration of study agent, during the trial, or within 6 months after the last administration of study agent.
- Positive pregnancy test at screening
- Female subjects who are breast-feeding or considering becoming pregnant during the study.
- Female subjects who do not use contraceptives.
- History of clinically significant drug or alcohol abuse in the last 12 months.
- Clinically significant abnormal screening laboratory results as evaluated by the investigator.
- Positive rheumatoid factor (RF) or anti-cyclic citrullinated peptide (anti-CCP) antibody at screening if the titers are crossing 3 times the upper limit of the normal.
- Subject with diagnosis and current symptoms of fibromyalgia.
- Any medical or psychological condition that, in the opinion of the investigator, could jeopardize or compromise the subject's ability to participate in this study.

### 6.1.4 Replacement of participants

Screen failures will be replaced by individuals that meet the inclusion criteria in order to reach the proposed target population of 147 patients.

Drop-outs will not be replaced.

### 6.1.5 Limitations for the participants

There are no specific limitations for the participants other than the ones listed at section 6.1.3 Exclusion criteria, with the exception that there is an obligation for female subjects to use contraceptives.

### 6.1.6 Advantages and disadvantages for the participants

In Belgium anti-TNF $\alpha$  treatment for axSpA is only reimbursed for patients with sacroiliitis on MRI according to ASAS and an elevated CRP. In this trial the European guidelines are used, so participants qualify for treatment with anti-TNF $\alpha$  if they have sacroiliitis on MRI (according to ASAS definition) or an elevated CRP (they do not have to meet both criteria) [11]. Up until now Golimumab is not reimbursed in Belgium for the treatment of axSpA. Thus, this means an advantage for the participants.

As all the investigations and treatments in this trial are considered routine clinical care, there are no specific disadvantages for the participants.

### General risks concerning the procedures included in the study protocol:

- Risk of blood sampling: hematoma at the puncture site, residual bleeding at the puncture site. Some patients may feel dizzy or faint during blood sampling. The qualified nurse who performs the blood sampling will act professionally in order to minimize these risks.
- Risk of ileocolonoscopy: this examination is generally safe. There is minimal risk of perforation of the intestinal mucosa.
- Risk of NMR: some patients may feel anxious because subjects are asked to lay flat in a small tunnel (claustrophobia). No risk for allergic reactions since no contrast agents are being used.

## 6.2 Study design and procedures

Cfr. infra: 6.3 Flowchart.

### 6.2.1 Screening visit

At the screening visit the informed consent form (ICF) will be signed and inclusion/exclusion criteria will be checked. Subsequently routine blood tests (complete blood count, electrolytes, liver function, kidney function, CRP and Erythrocyte Sedimentation Rate - ESR) and additional study samples for inflammatory and genetic markers will be taken (4x5mL serum and 3x4mL EDTA). These additional samples will be stocked pseudonymized in a prospective research biobank ("Biobank van menselijk lichaamsmateriaal van patiënten met reumatische en/of musculoskeletale aandoeningen en gezonde controles", EC 2019/0314, medical administrator: prof. dr. [name]). Also, HIV and hepatitis serology will be checked as part of the routine blood analyses and a Mantoux tuberculin skin test and a chest X-ray will be executed to exclude latent tuberculosis.

### 6.2.2 Baseline and follow-up

All subjects will undergo a baseline (pre-treatment) ileocolonoscopy to detect whether there is (subclinical) gut inflammation; this procedure is part of standard of care. Subjects must prepare for the ileocolonoscopy by avoiding consumption of high-fiber food or food rich in kernels from 3 days in advance.

Further preparation procedure for UZ Gent and the Reuma Institute Hasselt:

The day before the ileocolonoscopy, only liquid food is allowed. The evening before the examination, the subject needs to drink 1 portion of Plenvu in 500cc water and an extra 500cc of clear water. This needs to be repeated on the morning of the examination.

Further preparation procedure for Imelda hospital Bonheiden:

The day before the ileocolonoscopy at 12h a light meal is allowed, no fruit, no vegetables and no brown bread is allowed. Afterwards no food is allowed anymore, only drinking is allowed. And at 18h the subject needs to drink 2 portions of colofort in 2 liters water over 2 hours. On the morning at 7h the subject again needs to drink 2 portions of colofort in 2 liters water over 2 hours.

These preparations ensure an adequate cleaning of the intestines in order to optimize the endoscopists' view.

During the ileocolonoscopy, for all sites routine biopsies for pathological examination (4 biopsies in ileum, 8 biopsies in colon) and extra biopsies for RNA sequencing (2 biopsies in ileum, 2 biopsies in colon) will be taken. Additional for functional analyses, site specific (only in Ghent University Hospital), also 6 biopsies in ileum and 6 biopsies in colon will be taken. The investigators and the patient will be blinded for the results of this ileocolonoscopy until the subject is switched to golimumab. Only in case of major abnormalities necessitating medical intervention, the investigator will be made aware of the results of the ileocolonoscopy earlier. The central reader will make sure that 50% of the included patients will have subclinical gut inflammation and 50% of the patients will not have any subclinical gut inflammation. Additional blood samples will be drawn for functional analyses (site specific: only sampling of 4x10mL heparin blood in Ghent University Hospital) and 1 stool sample will be collected and stored pseudonymized in the prospective research biobank. After the trial has ended, all stool samples will be subject to biochemical and microbiome analyses (in one batch), performed by the laboratory attached to the department of Rheumatology of Ghent University Hospital.

At baseline, a treat-to-target principle will be installed. All subjects will receive a full anti-inflammatory dose NSAID for 2 weeks according to the routine clinical practice.

Visits are scheduled on week 0, 2, 4, 16, 28, 40 and 52 ( $\pm$  2 weeks). If subjects have a clinically important improvement, defined as an ASDAS score < 1.3 or a decrease of at least 1.1 in ASDAS score resulting in a maximum of 2.1, subjects will continue with the same treatment. If subjects do not meet this disease activity state after a treatment with the first NSAID, a different NSAID will be installed at full anti-inflammatory dose during 2 weeks. Again, if subjects have a clinically important improvement (compared to the baseline situation before initiating the first NSAID therapy) after 2 weeks treatment with the second NSAID, subjects continue with this treatment. If this disease activity state is not reached at week 4, the NSAID treatment will be stopped and subjects will start treatment with golimumab (anti-TNF $\alpha$  therapy, 50mg every 4 weeks, subcutaneous injection) in monotherapy. At every trial visit routine blood tests (inflammatory markers at week 0, 2, 4 and a complete blood count, electrolytes, liver function, kidney function, inflammatory markers at screening, week 16, 28, 40 and 52) will be performed. Additional study samples for inflammatory markers (2x5mL serum) will be taken at every trial visit (except for the baseline visit at week 0, no additional serum samples) and stored in the prospective research biobank. After 4 weeks NSAID treatment, after 6 months golimumab treatment and at time of relapse stool samples (1 sample at each time point) and additional blood samples (site specific: only sampling of 3x10mL heparin blood in Ghent University Hospital) will be collected. The additional heparin blood samples are used immediately for functional analysis; the stool samples are stored pseudonymized in the prospective research biobank. After the trial has ended, all stool samples will be subject to biochemical and microbiome analyses (in one batch), performed by the laboratory attached to the department of Rheumatology of Ghent University Hospital.

Maximal study duration for a subject is 12 months.

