### 6.2.3 Start of anti-TNF $\alpha$

If a subject starts on anti-TNF $\alpha$  treatment, the timing of the study visits will be recalculated: part B +12 weeks, +24, +36, etc.

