### **6.2.7 Procedures**

#### **6.2.7.1 Screening visit**

- ICF
- Check fulfillment of the inclusion and exclusion criteria
- Anamnesis
- Medical and family history
- Demographic data
- Symptom duration
- Current and past medication (NSAID): dosage and duration
- Clinical examination:
  - o weight, length, vital symptoms (blood pressure, heart frequency)
  - o BASMI
  - o Total tender and swollen joint count (TJC/SJC) (78)
  - o Dactylitis assessment
  - o MASES + plantar fascia + quadriceps and patellar tendon
- Assessment of work participation (site-specific: only in Ghent University Hospital).
- Questionnaires: Bath Ankylosing Spondylitis Disease Activity Index (BASDAI), Bath Ankylosing Spondylitis Functional Index (BASFI), Patient global assessment of disease activity, patient global pain assessment. Site-specific (only in Ghent University Hospital): Work Productivity and Activity Impairment (WPAI), health care consumption, EQ5D.
- Laboratory investigation (incl. 4x5mL serum + 3x4mL EDTA for additional research)
- Imaging: MRI SI joints (if not already done), chest X-ray
- Mantoux tuberculin test
- Pregnancy test for female subjects (on blood sample)

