#### **6.2.7.2 Baseline**

[figure not shown]
- Laboratory investigation (site-specific: only in Ghent University Hospital 4x10mL heparin blood for additional research)
- Stool sample
- Ileocolonoscopy including for all sites routine biopsies for pathological examination (4 biopsies in ileum, 8 biopsies in colon) and extra biopsies for RNA sequencing (2 biopsies in ileum, 2 biopsies in colon) will be taken. Additional for functional analyses, site specific (only in Ghent University Hospital), also 6 biopsies in ileum and 6 biopsies in colon will be taken.
- Start treat-to-target approach

[figure not shown]
- AND if baseline visit is performed more than 4 weeks after the screening visit:
  - o Anamnesis
  - o Current and past medication (NSAID): dosage and duration
  - o Clinical examination:
    - weight, length, vital symptoms (blood pressure, heart frequency)
    - BASMI
    - Total tender and swollen joint count (TJC/SJC) (78)
    - Dactylitis assessment
    - MASES + plantar fascia + quadriceps and patellar tendon
  - o Questionnaires: cfr. 6.2.7.1 (excl. WPAI, health care consumption and EQ5D)

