### 6.3 Flowchart

## 6.4 Study table

	Clinical examination (incl. BASMI)	Patient questionnaires	Blood: 4x5mL serum + 3x4mL EDTA	Blood: 2x5mL serum	Blood: 4x10mL heparin †	Pregnancy test (for female subjects)	Screening tuberculosis: chest X-ray and Mantoux	Stool sample	Ileocolonoscopy o	ASDAS	MRI SIG	Medication (golimumab) (starts after treatment failure on NSAIDs)
Screening	X	X	X			X	X			X	X *	
Baseline	X	X			X			X	X	X		
Follow-up visits	X	X		X						X		X (every 4 weeks)
Extra after 4 weeks NSAIDs					X (only 3 tubes)			X				
Extra after 6 months anti-TNF					X (only 3 tubes)			X				
Extra at remission					X (only 3 tubes, if and on same day as colonoscopy)				If first ileocolonoscopy was positive		X	
Extra at relapse	X	X		X	X (only 3 tubes)			X		X		

† Site-specific: only in Ghent University Hospital (Center 01); \* MRI SIG at screening if not already done in the context of diagnosis; o Ileocolonoscopy including for all sites biopsies for pathological examination (4 in ileum, 8 in colon) and RNA sequencing (2 in ileum, 2 in colon). Additional for functional analyses (site specific: only in Ghent University Hospital: 6 in ileum, 6 in colon).

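### Golimumab starts at week 4, but the last required blood count, chemistry and pregnancy test are from screening, at least 4 weeks earlier with no stated maximum

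*Combined protocol and SAP*

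**What the plan says.** **Start of golimumab.** Under section 6.2.2, a patient who has not reached the ASDAS target by week 4, after two NSAID courses of two weeks each, changes drug: "the NSAID treatment will be stopped and subjects will start treatment with golimumab".

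**Routine blood tests.** Section 6.2.1 requires the full panel at screening: "Subsequently routine blood tests (complete blood count, electrolytes, liver function, kidney function, CRP and Erythrocyte Sedimentation Rate - ESR". Section 6.2.2 then allocates tests to visits: "inflammatory markers at week 0, 2, 4 and a complete blood count, electrolytes, liver function, kidney function, inflammatory markers at screening, week 16", continuing to weeks 28, 40 and 52. Weeks 0, 2 and 4 carry inflammatory markers only. After a switch, section 6.2.3 resets the calendar: "the timing of the study visits will be recalculated: part B +12 weeks".

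**Pregnancy test.** It appears three times, each time tied to screening. The exclusion in section 6.1.3 is "Positive pregnancy test at screening". The screening procedures in section 6.2.7.1 list "Pregnancy test for female subjects (on blood sample". In the section 6.4 study table, the column "Pregnancy test (for female subjects" is marked in the screening row alone. The laboratory exclusion in section 6.1.3 likewise refers to screening results.

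**Screening to baseline.** No maximum interval is given. Section 6.2.7.2 adds procedures under the condition "AND if baseline visit is performed more than 4 weeks after the screening visit": history, medication, examination and questionnaires are then repeated. That repeat list names neither the routine panel nor a pregnancy test.

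**The concern.** The decision to give a first dose of a biologic is taken at a visit where the protocol asks for no current haematology, liver or kidney result and no pregnancy result. Section 6.5.9 advises against golimumab in pregnancy unless there is a clear need, and that judgement can be made only if the pregnancy is known. Section 6.5.8 lists raised transaminases as a common reaction and low white cells or platelets as uncommon. Yet the only required value to compare with the first on-treatment panel predates both the trial's NSAID courses and golimumab.

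What is at stake is patient safety at the first injection and a usable laboratory reference point for golimumab. The comparisons between patients with and without gut inflammation are not affected.

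**Working it through.** The protocol states no figure for this interval, so the check sets the schedule out and does interval arithmetic on it.

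**1. Tests required by visit** (sections 6.2.1, 6.2.2, 6.2.3, 6.2.7.1, 6.4)

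| Visit | Full routine panel | Inflammatory markers | Pregnancy test |
|---|---|---|---|
| Screening | yes | yes | yes |
| Week 0 | no | yes | no |
| Week 2 | no | yes | no |
| Week 4 (switch, first dose) | no | yes | no |
| Week 16, or switch + 12 weeks | yes | yes | no |

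Week 4 also has research serum, a stool sample and, in Ghent, heparin blood. None of these is a safety test.

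**2. Age of the tests at the first dose.** Let g be the screening-to-baseline interval in weeks.

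- Nominal age = g + 2 + 2 = g + 4 weeks (two NSAID courses of 2 weeks).
- With the upper end of the ±2-week visit window: g + 6 weeks.
- g = 0: 4 to 6 weeks.
- g = 4: 8 to 10 weeks. Section 6.2.7.2 allows g above 4, so the nominal age can exceed 8 weeks, and no upper limit is stated.

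Read literally, the window could also put the week 4 visit as early as 2 weeks after baseline. That would cut the two NSAID courses short, and there would still be no panel before the dose.

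**3. Gap between consecutive full panels.** (g + 4) + 12 = g + 16 weeks, so at least 16 weeks nominally, with the first dose in between. Injections before the second panel fall at switch weeks 0, 4 and 8: 3 × 50 mg = 150 mg.

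**4. Pregnancies beginning between screening and first dose.** The protocol gives neither the sex split nor a contraceptive failure rate, so both are assumptions: 30% to 50% women, and 1% to 5% pregnancies per year on contraception. Section 10.1 plans 110 golimumab patients, so 0.30 × 110 = 33 to 0.50 × 110 = 55 women. Expected number = women × yearly rate × test age / 52:

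- low: 33 × 0.01 × 4/52 = 0.03
- high: 55 × 0.05 × 8/52 = 0.42

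The estimate takes no credit for excluding women who are considering pregnancy or for history-taking at each visit, so the number that would go unrecognised is lower. It rises in proportion if the screening-to-baseline interval is longer.

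**The case against.** **No standard is breached.** Nothing in the protocol says that a panel or pregnancy test 4 to 6 weeks old is too old for a first dose. Section 6.1.6 describes the investigations as routine care, and a physician may order more. Contraception is mandatory, women considering pregnancy are excluded, and history, medication review and examination take place at each follow-up visit. All of this stands, and it is why the point is modest. These measures lower the risk, but they do not detect a pregnancy or supply a laboratory value. The protocol's own practice also points towards renewal: it repeats the clinical assessments once more than 4 weeks separate screening from baseline.

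**The tests may be listed elsewhere.** The flowchart (section 6.3) and two figures within the section 6.2.7.2 list are not shown. The generic laboratory entries in sections 6.2.7.2 and 6.2.7.3 do not itemise routine tests. The study table has no column for the routine panel, so it supports only the pregnancy point. This limits certainty. Even so, section 6.2.2 assigns routine tests visit by visit and gives no full panel at weeks 0, 2 or 4.

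**Stronger readings that the documents do not support.**

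- *Section 9 is contradicted.* A reader might infer that its 24-hour pregnancy reporting implies surveillance, or that it requires laboratory changes to be dated against the first dose. The reporting duty runs from becoming aware. The first-intake boundary decides where medical events are recorded and says nothing about dating laboratory values. It is also unclear that trial medication means golimumab alone, since section 6.5 lists NSAIDs beside it.
- *The frequency bands measure the harm.* A reader might apply the section 6.5.8 bands to 110 patients and count the results as harm from the missing panel. Those bands count drug reactions, with no 12-week horizon. The relevant quantity is abnormalities arising between screening and the first dose, and the protocol gives no basis for estimating it.

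**Conclusion.** The point holds as a modest safety improvement. On the text available, the protocol requires no full panel and no pregnancy test between screening and the first golimumab injection. The interval is nominally at least 4 weeks, more than 8 weeks if baseline falls more than 4 weeks after screening, and has no stated maximum. The next full panel follows three injections.

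Few unrecognised pregnancies are expected: well under one in the whole trial on the assumed rates. The number of laboratory abnormalities arising before the first dose cannot be estimated from the documents. The primary inference is unaffected. The conclusion assumes that section 6.2.2 governs the content of the routine tests and that the parts not shown add no test at the switch.

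**What to change.** Amend sections 6.2.2 and 6.2.7.3 and the study table in section 6.4 so that, at the visit where the switch to golimumab is decided:

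- the existing full routine panel is taken and, for women, the existing serum pregnancy test;
- the investigator reviews the results before the first injection, with a retest allowed for a transient laboratory abnormality;
- the results are recorded as the pre-golimumab safety baseline.

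Nothing further is needed. The gap shown does not call for an infection-clearance step, a longer NSAID course, a permanent bar on golimumab after one abnormal result, or a new analysis rule.

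**Cost.** Blood is already drawn at week 4 and both tests are already in the protocol, so the burden is a short amendment, possibly one extra tube and a few days' wait. The wait has to fit the ±2-week window, because 4 weeks plus the 48 weeks of golimumab in section 6.2.6 already makes 52 weeks, the 12-month maximum.

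An occasional patient may not start, and section 6.1.4 does not replace drop-outs. The effect on the section 10.1 comparison is small. By normal approximation at two-sided 5%, 55 per group at 80% power implies a standardised difference of (1.960 + 0.842)/√(55/2) = 0.534. Power is then Φ(0.534 × √(n/2) − 1.960), with losses split equally between groups. One patient lost (n = 54.5 per group) gives 79.6%. Six lost (n = 52, about 5% of 110, an assumed upper figure) gives 77.8%.
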